Our target population consists of patients with a known diagnosis of cancer who were seen at the study site after Aug 1, 2021. Our study will employ the following inclusion criteria:

- Above the age of 18
- Meet one of the sub-criteria below:
 - Meet the CDC definition for immunocompromised status for cancer patients, i.e patients receiving active treatment for solid tumor or hematologic malignancy OR
 - Be a recipient of stem cell transplant or CAR-T cell therapy in the last 2 years OR
 - Have a negative SARS-CoV-2 spike IgG despite standard vaccination series, irrespective of active/inactive cancer status, on observation, or active therapy.
- Underwent an in-person encounter at a study facility during the study period
- Have received the second of the mRNA vaccines (BNT162b2 or mRNA 1273) or the adenoviral Ad26CoV2.S vaccine at least 28 days before the booster dose.

Exclusion Criteria

- Patients who have had a serious adverse reaction to any prior COVID-19 vaccines resulting in emergency room visit or hospitalization, had events related to myocarditis, thrombosis and thrombocytopenia syndrome or anaphylaxis to any prior dose of the COVID-19 vaccines.
- Patients who have had a documented COVID-19 infection in the 90 days prior to starting the study

Outcomes

We will be studying the following primary outcome:

- Rates of seroconversion for SARS-CoV-2 spike antibody after 4 weeks after a booster dose of BNT162b2/mRNA-1273 COVID Vaccine in patients that were initially seronegative after standard vaccine series

We will be studying the following secondary outcomes:

- Safety of booster dose of BNT162b2 and mRNA 1273 vaccines
- Correlation between malignancy type and prior treatment type and seroconversion
- Correlation between timing of most recent cancer-directed treatment and seroconversion
- Correlation between the total number of cancer-directed treatments received and seroconversion
- Differences between booster efficacy dependent on prior vaccine type (mRNA vs. adenoviral, BNT162b2 versus mRNA-1273)
- T cell responses at baseline and 4 weeks following vaccination
- Antigen neutralization assay results at baseline and 4 weeks following vaccination

Duration of sustained immunogenicity following vaccination in seropositive patients following our cohort for 24 months following booster vaccinations

Cohort 2

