On December 16, 2021 the CDC published updated recommendations regarding use of the Ad26.COV2.S (Johnson & Johnson) vaccine (<https://www.cdc.gov/media/releases/2021/s1216-covid-19-vaccines.html>) due to the rare but persistent adverse event thrombosis with thrombocytopenia syndrome (TTS) seen with the Ad26.COV2.S vaccine alone. They expressed a clinical preference for individuals to receive an mRNA COVID-19 vaccine over an Ad26.COV2.S vaccine, however, reaffirmed that receiving any vaccine is better than being unvaccinated. This recommendation, however, did not specify stipulations for our currently immunosuppressed patients with cancer population who have already received three prior mRNA COVID-19 vaccines with minimal or no response. Given our patient population remains at high-risk for severe COVID-19 despite three prior mRNA COVID-19 vaccines, we feel the administration and efficacy evaluation of Ad26.COV2.S (Johnson & Johnson) vaccine as a mix and match strategy for booster vaccination continues to remain warranted as part of our study. In fact, a recent study from South Africa does suggest excellent efficacy of a booster Ad26.COV2.S vaccine corroborating this approach¹⁵.

Some patients, however, remain hesitant to receive an Ad26.COV2.S given its rare but potentially severe adverse event as outlined above. Thereby, for study candidates who prefer not be randomized in cohort 2, participation in cohort 3 will be offered. Cohort 3 will be a prospective, non-randomized cohort to address the question of whether a switch mRNA vaccine approach might be more effective at achieving an increased immune response in poor responders to a prior series of three mRNA vaccinations (mRNA-1273 (Moderna) or BNT162b2 (Pfizer/BioNTech)). Eligible patients will be prospectively followed to receive a BNT162b2 vaccine as a fourth dose evaluating their increase in mean SARS-CoV-2 Spike IgG titers above a pre-established threshold by 4 weeks following vaccination as the primary endpoint with further secondary endpoints regarding safety, neutralization antibody and T cell assays and durability of response with assessments at 3, 6, 12 and 24 months. As it is anticipated that about 60-70% of study candidates will have previously received BNT162b2 and 30-40% mRNA-1273, this cohort will allow an assessment of a switch approach in a non-randomized single arm fashion.

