Patients will undergo spike antibody testing at D0 of the study and then return for a study visit four weeks after their booster vaccine to complete a SARS-CoV-2 spike antibody test and T cell response assays to determine virus neutralizing activity. Side effects to the booster dose will be noted via a questionnaire that patients would fill out at this visit which will collect data pertaining to side effects and their severity compared to prior vaccine doses. Patients will return for a final study visit five to six months after their booster vaccine to assess for long-term side effects and to obtain SARS-CoV-2 spike antibody test and T cell response assays in patients who became seropositive after 4 weeks to determine if immunogenicity is sustained.

Follow up tests for cohorts 2 and 3: Patients will undergo spike antibody testing as well as baseline laboratory studies including CBC, lymphocyte subsets, quantitative immunoglobulins, T-cell response and neutralizing activity at enrollment. Patients will then receive their 4th booster vaccine (D0). Patients will return for a study visit at least 28 days after their booster vaccine to complete a SARS-CoV-2 spike antibody

test including follow-up laboratory studies as listed above. Side effects to the booster dose will be noted via a questionnaire that patients would fill out at this visit which will collect data pertaining to side effects and their severity compared to prior vaccine doses. Patients will then return for further study visits at 3 months, 6 months and 12 months and then a final study visit 24 months after their booster vaccine to assess for long-term side effects and to obtain SARS-CoV-2 spike antibody test, T cell response assays, and other laboratory studies as above in patients who became seropositive after 4 weeks to determine if immunogenicity is sustained.

Sample size

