Cohort 3. Our null hypothesis is that the additional homologous booster vaccine dosing with the BNT162b2 after prior BNT162b2 vaccination will increase mean titers in the spike IgG assay by at least 300%. Alternate hypothesis is that heterologous vaccination with the BNT162b2 after prior mRNA-1273 vaccination will increase mean titers by an additional 300%- that is to 600%. To achieve 80% power at a significance level alpha = 0.05, a one sided two sample t-test would require 22 samples per group to detect differences in mean titers of 750 AU/mL and 1500 AU/mL at an estimated standard deviation of 1000 AU/mL. Given we estimate 30-40% patients with have had prior mRNA-1273 vaccination and accounting for 5% dropout rate, we will thus use a planned sample size of 80.

Statistical analysis

To assess our goals as outlined above, statistical analysis will be done in the R software environment. The primary aim of cohorts 1 and 2 examining the seroconversion rates after 4 weeks will be checked with a one sample z test of proportions. The primary aim of cohort 3 examining the increase in mean Spike IgG titers will be checked with a one sided two sample t-test. Secondary aims involving the significance of associations between certain malignancies and the rates of seroconversion in our prospective single arm study will be measured by Fisher's exact and Cochran- Mantel-Haenszel tests depending on if analysis is conducted by a stratified variable (Cochran- Mantel-Haenszel) or not (Fisher's exact). The more complicated relationship between patients' seroconversion rates, their recent receipt of medical treatment, and additional factors such as history of malignancy will be examined through a multivariate logistic

regression model. After addressing the appropriateness of interaction terms, a Wald test will be used to consider the statistical significance of all included variables at the $p < 0.05$ level.

Duration

Our study will follow patients from Aug 1, 2021 through November 2023, which will allow for sufficient time to assess follow-up serologies after COVID-19 vaccination infection in patients with cancer (24 months follow up).

Matching

Cohort 1

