Assessment		Screening	Initial visit	Vaccine day (D0)	D28	D150-180
Informed consent	ICF	X	X			
Demographics	Demographics	X				

	Medical history	X				
	COVID vaccine history	X				
	Inclusion/Exclusion Criteria	X				
	SARS-CoV-2 Spike antibody	X				
Safety	Vital signs		X		X	X
	SpO2		X		X	X
	Physical exam		X	X	X	X
	Document Side effects				X	X
	Side Effect Questionnaire				X	
Intervention	Vaccine administration			X		
	Vaccine questionnaire				X	
Outcome	SARS-CoV-2 Spike antibody		X		X	X
	SARS-CoV-2 Neutralization assay		X		X	X
	EUROIMMUN T-cell assay		X		X	X

Study calendar cohort 2

Assessment		Screening	Initial visit	Vaccine day (D0)	D28	D90	D180	D365	D730
Informed consent	ICF	X	X						
Demographics	Demographics	X							
	Medical history	X			X	X	X	X	X
	COVID vaccine history	X			X	X	X	X	X
	Inclusion/Exclusion Criteria	X							
	SARS-CoV-2 Spike antibody	X							
Intervention	Vaccine administration			X					
	Vaccine/safety questionnaire				X	X	X	X	X
Outcome	SARS-CoV-2 Spike antibody		X		X	X	X	X	X
	SARS-CoV-2 Neutralization assay		X		X	X	X	X	X
	EUROIMMUN T-cell assay		X		X	X	X	X	X

For study visits a 7 day window will be allowable for the 4 week follow up visit, a 14 day window will be allowable for the day 90 visit and 28 day window will be allowable for the rest of the study visits.

Study calendar cohort 3

Assessment		Screening	Initial visit	Vaccine day (D0)	D28	D90	D180	D365	D730
Informed consent	ICF	X	X						
Demographics	Demographics	X							
	Medical history	X			X	X	X	X	X
	COVID vaccine history	X			X	X	X	X	X
	Inclusion/Exclusion Criteria	X							
	SARS-CoV-2 Spike antibody	X							
Intervention	Vaccine administration			X					
	Vaccine/safety questionnaire				X	X	X	X	X
Outcome	SARS-CoV-2 Spike antibody		X		X	X	X	X	X
	SARS-CoV-2 Neutralization assay		X		X	X	X	X	X
	EUROIMMUN T-cell assay		X		X	X	X	X	X

For study visits a 7 day window will be allowable for the 4 week follow up visit, a 14 day window will be allowable for the day 90 visit and 28 day window will be allowable for the rest of the study visits.

External Site

Institution	Point of Contact	Role
EUROIMMUN	[name], [contact]	Reagents and supplies, running samples.
International Cancer Covid Vaccination Consortium	Crick Legal [contact]	Data Sharing with ICCV. DUA will be reviewed and executed to account for this activity.

References:

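### Follow-up ending in November 2023 cannot provide the planned 24-month durability data for cohort 3 or later cohort 2 patients, and cohort 1 has no visit after day 150-180

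*Combined protocol and SAP*

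**What the plan says.** **End of follow-up.** The Duration section says "Our study will follow patients from Aug 1, 2021 through November 2023" and describes this as sufficient for serology "in patients with cancer (24 months follow up").

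**Cohorts 2 and 3.** The Methods text on follow-up tests plans visits at 3, 6 and 12 months, "then a final study visit 24 months after their booster vaccine". Both study calendars carry a D730 column with spike antibody, neutralization and T-cell assays. The note under each calendar adds that a "28 day window will be allowable for the rest of the study visits", after giving shorter windows for the 4-week and day-90 visits.

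**Origin of cohort 3.** Its introduction begins "On December 16, 2021 the CDC published updated recommendations regarding use of the Ad26.COV2.S" and explains that the cohort is for candidates who, given the safety concern behind that update, prefer not to be randomized in cohort 2.

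**Cohort 1.** The last of its secondary outcomes is "Duration of sustained immunogenicity following vaccination in seropositive patients following our cohort for 24 months following booster vaccinations". The Methods text for cohort 1 says "Patients will return for a final study visit five to six months after their booster vaccine", and the cohort 1 calendar ends with a D150-180 column.

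The document gives no opening date for cohort 2 or cohort 3, no end of accrual, and no extension of follow-up beyond November 2023.

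**The concern.** Two separate inconsistencies affect the same outcome.

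First, a fixed calendar end gives 24 months only to patients vaccinated at least 24 months before it. The Duration section starts its count on 1 August 2021, which suits the first cohort 1 patients. Cohort 3 came later, and the end date does not allow for that.

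Second, cohort 1 declares a 24-month outcome that its own visit schedule cannot supply, whatever the end date.

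The loss is a declared time point of a named secondary outcome. If the plan is followed as written, 24-month data could come almost entirely from the earliest cohort 2 patients, a group picked out by calendar time and not by design. The Data and Safety Monitoring Plan also relies on questionnaires at every cohort 2 follow-up visit to screen for thrombosis with thrombocytopenia, so patients dosed later would lose their last planned safety contact too.

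**Working it through.** **Inputs**
- Study period: 1 August 2021 to November 2023 (Duration). I take 30 November 2023 as the end, the reading most favourable to the plan.
- Final visit for cohorts 2 and 3: day 730, with a 28-day window (calendars). The direction of the window is not stated. I assume it may be used before the visit, so the earliest acceptable day is 730 − 28 = 702. This also favours the plan.
- Earliest cohort 3 dose: 17 December 2021, the day after the recommendation that prompted the cohort. This is an inference, since no opening date is given.
- Planned sizes: up to 250 in cohort 1 and 80 in cohort 3 (Sample size).
- Months are days divided by 30.4375.

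**The plan's own figure.** From 1 August 2021 to 30 November 2023 is 851 days, or 28.0 months. The stated 24 months therefore holds for a patient dosed on the first day, with about 4 months to spare. It does not hold for later patients.

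**Latest dose date that allows a 24-month visit** (study end minus required days)

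| Study end | Nominal day 730 | Day 702 (full early window) |
|---|---|---|
| 30 Nov 2023 | 30 Nov 2021 | 28 Dec 2021 |
| 1 Nov 2023 | 1 Nov 2021 | 29 Nov 2021 |

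**Cohort 3**
- A dose on 17 December 2021 has nominal day 730 on 17 December 2023, after the stated end. By 30 November 2023 that patient has 713 days, or 23.4 months. No cohort 3 patient reaches day 730.
- An in-window visit (days 702-713) is possible only for doses from 17 to 28 December 2021, which is 12 calendar days in which to accrue 80 patients.
- If the end is 1 November 2023, the limit of 29 November 2021 comes before the cohort existed, and nobody qualifies.
- The cohort 3 rationale cites reference 15, a preprint whose doi contains 2021.12.28. If that string is a date, the text was completed no earlier than 28 December 2021, which leaves at most one qualifying day.

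**Follow-up available by 30 November 2023 for later doses (assumed dates)**

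| Dose date | Days | Months |
|---|---|---|
| 1 Feb 2022 | 667 | 21.9 |
| 31 Mar 2022 | 609 | 20.0 |
| 30 Jun 2022 | 518 | 17.0 |

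**Cohort 2.** The same limits apply: patients dosed by 30 November 2021 (28 December 2021 with the window) can have the visit, and later ones cannot. The split cannot be computed without accrual dates.

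**Cohort 1.** The last scheduled sample is at 150/30.4375 = 4.9 to 180/30.4375 = 5.9 months, against an outcome horizon of 24 months. Scheduled 24-month samples: 0 of up to 250. Patients boosted by November 2021 have the calendar time but no visit, so moving the end date would not help this cohort.

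**The case against.** The strongest reply is that the loss is narrower than it sounds. Several parts of it stand:

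- **Cohort 2 may be partly spared.** Its opening date is not given, and the safety plan's wording suggests it was already running when the December 2021 update appeared. Some of its patients may well reach day 730.
- **Only the last time point is lost in cohorts 2 and 3.** Their formal outcome lists name durability without a 24-month horizon; the horizon comes from the cohort introductions, the Methods text and the calendars. Anyone dosed by 30 November 2022 still reaches day 365, so the 3-, 6- and 12-month assessments survive for them.
- **The durability group is smaller than the full cohorts.** It is limited to patients who became seropositive, so 250 and 80 are upper limits on the number affected. The arithmetic is the same for that subset.
- **The loss is administrative.** In randomized cohort 2, dosing date should not depend on arm, so the cut-off in itself costs precision and does not bias the comparison between arms.
- **The primary endpoints are at 4 weeks**, and the study describes itself as exploratory.

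It could also be said that November 2023 is approximate, or that the day-730 visits will take place regardless. The first does not help: if the last dose were given on 30 June 2022 (assumed), day 730 would be 29 June 2024, about seven months past the stated end. The second concedes that the Duration section is wrong.

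**Conclusion.** The concern holds. For cohort 3 the stated end rules out nominal day 730 for every patient, and allows an early in-window visit only for doses on about 17-28 December 2021. For cohort 2 the visit is ruled out for anyone dosed after 28 December 2021, in unknown number. For cohort 1 no patient has a sample scheduled after about 6 months, although the outcome runs to 24.

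The cohort 3 result rests on inferring its start from the December 2021 recommendation; the 12-day figure also assumes a 30 November 2023 end and a window that extends before the visit. The cohort 1 result needs no assumption, because the outcome and the schedule contradict each other directly. This should be corrected, but it does not threaten the primary analyses.

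**What to change.** **Cohorts 2 and 3.** In the Duration section, replace November 2023 with the last enrolled patient's day-730 visit plus its 28-day window, and state whether the window runs before the visit, after it, or both. Accrual dates are not given, so as illustrations:

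| Assumed last dose | Day 730 | Plus 28 days |
|---|---|---|
| 31 Jan 2022 | 31 Jan 2024 | 28 Feb 2024 |
| 30 Jun 2022 | 29 Jun 2024 | 27 Jul 2024 |
| 31 Dec 2022 | 30 Dec 2024 | 27 Jan 2025 |

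**Cohort 1.** Reconcile the outcome with the schedule. Either restate the durability outcome as 5-6 months, or add the later sampling visits that a 24-month outcome requires to the Methods text and the cohort 1 calendar.

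**Cost.** The smallest correction is an amendment to one date and one outcome line. The day-730 visits in cohorts 2 and 3 are already planned, so the amendment adds no visits there, although the study stays open longer. Restating cohort 1's horizon needs no new work but gives up about 18 months of a declared outcome (24 minus about 6). Adding visits keeps the outcome, at the price of further samples, assays and patient contact.

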Have received an FDA authorized booster dose of mRNA (BNT162b2 or mRNA 1273) vaccine at least 28 days before study enrollment

Exclusion Criteria

Patients who have had a serious adverse reaction to any prior COVID-19 vaccines resulting in emergency room visit or hospitalization, had events related to myocarditis, thrombosis and thrombocytopenia syndrome or anaphylaxis to any prior dose of the COVID-19 vaccines.

Patients who have had a documented COVID-19 infection in the 90 days prior to study enrollment

Outcomes

Primary outcome: Rates of seroconversion for SARS-CoV-2 spike antibody after 4 weeks following an additional booster dose of BNT162b2/AdCov2.S COVID vaccine in patients that had a poor serological response after standard vaccine series (allowing additional booster dose)

Secondary outcomes: Safety of booster dose of BNT162b2 and AdCov2.S vaccines, correlation between malignancy type and prior treatment type and seroconversion, correlation between timing of most recent cancer-directed treatment and seroconversion, correlation between the total number of cancer-directed treatments received and seroconversion, differences between booster efficacy dependent on prior vaccine type (BNT162b2 versus mRNA-1273), T cell responses at baseline and 4 weeks following vaccination, Antigen neutralization assay results at baseline and 4 weeks following vaccination, duration of sustained immunogenicity following vaccination in seropositive patients, correlations with baseline immune status correlates such as lymphocyte subsets/immune globulin levels

Safety monitoring.

Patients who have met all eligibility criteria will then be randomized 1:1 to receive either the BNT162b2 or AdCov2.S and then will be scheduled to receive their study dose at the Montefiore Vaccine Center. Each patient will be observed for a minimum of 15 minutes after their vaccination to monitor for any adverse

effects in the Montefiore Vaccine Center as per the Vaccine Center protocol.

Cohort 3

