Cohort 1. For a 1 sample test of proportions our hypothesis is that booster vaccine dosing will induce detectable immunity by the spike IgG assay in at least 20% of individuals. Null hypothesis is a positivity rate of 10% to account for some test variability and therefore the alternative hypothesis is $p > 30\%$. Our planned sample size of up to 250 will have ample power ($>95\%$) to detect such a difference in our primary endpoint and will still retain 80% power and 5% significance in the secondary preplanned subset analyses as long as cohort sizes per subset are >26 . We anticipate the large majority of patients will be hematologic malignancy patients and such preplanned subset analyses will include two cohorts, the highly immune suppressed (prior anti- CD20, CAR-T, or SCT therapy), and all others (solid tumor/hematologic malignancy patients) who do not fall into the first cohort. We anticipate cohort sizes of at least 26 per cohort based on the numbers of seronegative patients identified in our prior study.

Cohort 2. Our null hypothesis is that the additional homologous booster vaccine dosing will induce detectable immunity (positive spike IgG test result higher than the predefined threshold for seropositivity—i.e. >1000 AU/ml) by the spike IgG assay in at least 25% of individuals. Alternate hypothesis is that heterologous vaccination with the AdCov2.S vaccine will increase this seroconversion rate by an additional 25%- that is to 50%. With an alpha of 0.05 and 80% power to detect the difference, we would require a sample size of 46 in each group. Accounting for 5% dropout rate, we will thus use a planned sample size of up to 100 subjects. We anticipate the large majority of patients will be hematologic malignancy patients and such preplanned subset analyses will include two cohorts, the highly immune suppressed (prior anti-CD20, CAR-T, or SCT therapy), and all others (solid tumor/hematologic malignancy patients) who do not fall into the first cohort.

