Patients would serve as their own control. Baseline seropositivity rate by definition is 0% for the cohort but anticipating natural and laboratory variation we have based on statistical null hypothesis around a 10% seropositivity rate at 4 weeks and anticipate that booster vaccination will increase this to higher than 30%.

Planned intervention

Cohort 1

The planned intervention is to administer a booster dose of the BNT162b2 (Pfizer/BioNTech) or mRNA-1273 (Moderna) vaccine to patients that meet FDA/CDC criteria of cancer on active therapy or patients that have received a stem cell transplantation or CAR-T cell therapy in the last 2 years or those that have a negative spike IgG after having = completed one of the FDA's Emergency Use Authorized vaccination series for COVID-19 (i.e. 2 doses of the mRNA-based mRNA-1273 (Moderna), BNT162b2 (Pfizer/BioNTech), or a single dose of the adenovirus-based Ad26.COV2.S (Johnson & Johnson) vaccine, following completion of their vaccination series.

Cohort 2

The planned intervention is to administer an additional booster dose of the BNT162b2 (Pfizer/BioNTech) or Ad26.COV2.S (Johnson & Johnson) vaccine to patients that meet eligibility criteria for cohort 2 in a 1:1 randomization fashion with negative spike antibody vs. low positive antibody level serving as a stratification factor to ensure controlling for key confounder.

Cohort 3

The planned intervention is to administer an additional booster dose of the BNT162b2 (Pfizer/BioNTech) vaccine to patients that meet eligibility criteria for cohort 3 in a prospective single arm fashion in patients that had a poor serological response after standard vaccine series (including a third dose).

Participant recruitment

The study will both utilize data from the electronic health record to identify patients meeting the above inclusion criteria and enroll them on to the study and accept patients self-referred or referred by their provider at Montefiore Medical Center or external institutions. A consenting visit will be scheduled with each prospective patient. Following a carefully conducted and documented informed consent process subjects who consent for study participation will then be screened. Patients who qualify for booster COVID-19 vaccination as per FDA/CDC guidance and study criteria will then participate in our study.

Data and Safety Monitoring Plan

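### The cohort 2 primary analysis names no adjustment for prior anti-CD20, CAR-T or SCT therapy, its own preplanned subset factor, or for the antibody stratum used in randomisation

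*Combined protocol and SAP*

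**What the plan says.** **Randomisation.** In the safety monitoring text for cohort 2: "Patients who have met all eligibility criteria will then be randomized 1:1 to receive either the BNT162b2 or AdCov2.S". The Planned intervention section (Cohort 2) adds one factor, "with negative spike antibody vs. low positive antibody level serving as a stratification factor to ensure controlling for key confounder". No other factor is named.

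**Subset factor.** The Sample size section defines, in the cohort 1 paragraph, two preplanned subsets: "the highly immune suppressed (prior anti- CD20, CAR-T, or SCT therapy), and all others". The cohort 2 paragraph repeats the same split. The cohort 2 study calendar lists medical history at Screening, so prior therapy of these kinds should be obtainable before allocation.

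**Size.** "With an alpha of 0.05 and 80% power to detect the difference, we would require a sample size of 46 in each group", for 25% versus 50%. "Accounting for 5% dropout rate, we will thus use a planned sample size of up to 100 subjects".

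**Analysis.** Under Statistical analysis, the primary aim of cohorts 1 and 2 "will be checked with a one sample z test of proportions". CMH and Fisher's exact tests are assigned to secondary associations between malignancies and seroconversion. A multivariable logistic model is assigned to the relation of seroconversion with recent treatment and other factors. Neither is given as the primary comparison of the two vaccines.

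**The concern.** The plan treats two baseline factors as important in cohort 2. One is called the key confounder and is used in the allocation. The other divides the population for the preplanned subset analyses, and the name given to that group suggests a weaker expected response. The primary analysis uses neither.

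Two things follow if these factors predict response:

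- An unadjusted comparison of about 46-50 patients per arm carries avoidable noise from chance differences in the share of highly immunosuppressed patients.
- A test that ignores a factor used to stratify the randomisation is somewhat conservative, so part of the benefit of stratifying is given away.

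If the analysis is not fixed in advance, an uneven split also invites an argument after the data are seen about whether to adjust.

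**Working it through.** **1. The plan's own figure.** With p1 = 0.25, p2 = 0.50 and mean 0.375, the pooled-variance formula is

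n = [z(1-α)·√(2·0.375·0.625) + z(0.80)·√(0.25·0.75 + 0.50·0.50)]² / 0.25²

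- One-sided 0.05: (1.645·0.6847 + 0.8416·0.6614)² / 0.0625 = 45.3, so 46 per group. This matches the plan.
- Two-sided 0.05: 57.7, so 58 per group; 46 per group then gives about 70% power.

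The plan does not state sidedness for cohort 2, so the one-sided version is used below.

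**2. Size of chance imbalance.** Inputs assumed, because the documents give none: prevalence p of the highly immunosuppressed group, and independence from antibody level. With n per arm and the total fixed, the SD of the between-arm difference in that share is 2·√[p(1-p)/(2n-1)].

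- n = 50, p = 0.5: 2·0.5/√99 = 10.1 points. With p = 0.3 or 0.7: 9.2 points.
- n = 46, p = 0.5, exact hypergeometric: a difference of 10 points or more in 29.7% of trials, and of 20 points or more in 6.0%.

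The shift in the observed vaccine difference is the imbalance times the response gap between subsets. A 10-point imbalance with a 30-40 point gap gives 0.10 × 0.30 to 0.10 × 0.40, or 3-4 points, against the design difference of 25. Over all randomisations the shifts average to zero.

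**3. What adjustment gains, and what stratified allocation gains.** 40,000 simulated trials per scenario, 46 per arm, half highly immunosuppressed, one-sided 0.05. Each scenario averages to 25% versus 50%. Unadjusted is the pooled two-proportion z test; adjusted is CMH over the therapy factor. Allocation is either not stratified or stratified on that factor.

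| BNT162b2 (suppressed/other) vs Ad26.COV2.S | Not stratified: unadjusted | Not stratified: adjusted | Stratified: unadjusted | Stratified: adjusted |
|---|---|---|---|---|
| 15%/35% vs 38%/62% | 81.7% | 82.4% | 82.4% | 82.8% |
| 10%/40% vs 30%/70% | 81.3% | 85.7% | 83.0% | 85.2% |
| 5%/45% vs 25%/75% | 81.4% | 89.1% | 84.7% | 89.2% |

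The subset gaps in the three rows are 20-24, 30-40 and 40-50 points. Adjustment without stratified allocation gains 0.7, 4.4 and 7.7 points. Once the analysis is adjusted, stratifying the allocation as well changes power by half a point or less. Two-sided, the middle row goes from 70% to 77%.

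With 70-80% of patients highly immunosuppressed and a 20-point gap, adjustment gains nothing (81.2% to 81.3%, and 81.6% to 81.5%).

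**4. Validity.** Under the null, with 50 per arm, half highly immunosuppressed and a 30-point gap, the one-sided type I error is:

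- allocation not stratified on the factor: 5.2% unadjusted, 5.1% CMH;
- allocation stratified on the factor: 4.2% unadjusted, 5.2% CMH.

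The mean estimate is 0 under the null and 0.25 under the alternative. The first line is the position of the therapy factor in this plan: ignoring it is valid. The second shows what happens to a factor that is used in allocation but ignored in analysis, as antibody level is here. If antibody level predicts response that strongly, the unadjusted test is conservative and CMH restores the nominal level.

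**The case against.** A preplanned subset need not be a randomisation stratum, and one stratification factor for up to 100 patients is an ordinary choice. A reader might infer that the randomisation is deficient or the vaccine comparison confounded. The documents and the arithmetic do not support that: chance imbalance biases nothing on average, and type I error stays near 5%. Uneven subset arms matter little too: a 20 versus 26 split keeps 98% of the information of 23 versus 23.

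The imbalance figures in step 2 are also at the no-correlation end. If highly immunosuppressed patients are more often antibody-negative, the existing stratification already balances part of the factor. Take half the patients as antibody-negative. The chance of a 10-point or larger imbalance then falls from 30% to 26% if 70% of the negative and 30% of the low-positive patients are highly immunosuppressed, to 19% at 80%/20%, and to 9% at 90%/10%. This stands. The power gain largely survives it: in the 10%/40% versus 30%/70% scenario, power was 82% unadjusted and 85-86% adjusted at correlations of 0.3-0.5 between the two factors.

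A reader might also infer that therapy history is ignored altogether. It is not. Prior treatment type is a secondary outcome for cohort 2, and the logistic model covers treatment factors. But neither is the primary vaccine comparison.

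Finally, a one-sample test compares no arms, so there is as yet no comparison in which to adjust. That is a separate and larger problem. The covariates should be chosen when it is corrected.

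**Conclusion.** The point holds as a modest matter of precision in the analysis. The cohort 2 primary analysis names no adjustment for a baseline factor that the plan prespecifies and can obtain at Screening, nor for the factor on which it randomises. Under the assumptions in step 3, adjusting for therapy history raises power from about 81-82% to 82-89%. The gain is about 0-1 points when the subsets differ by about 20 points, and 4-8 points when they differ by 30-50.

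The prevalence, the response gaps and the independence from antibody level are all assumed. That the highly immunosuppressed group responds less in cohort 2 is an inference from its label; the plan gives no subset response rates. That antibody level is the only stratification factor is read from the absence of any other. Nothing here makes the randomisation as planned invalid.

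**What to change.** When the cohort 2 primary test is specified as a two-arm comparison, make it a CMH test stratified by baseline antibody level (negative, low positive) and by prior anti-CD20, CAR-T or SCT therapy (yes, no), or a logistic model with both as covariates. Take the therapy factor from the Screening medical history. Report a stratified difference in proportions with it, so that the result can be read against the 25-point design difference. State the sidedness in the same sentence.

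Adding the therapy factor to the randomisation is optional. It helps the look of the baseline table but adds almost no power once the analysis is adjusted. If randomisation has already begun, the analysis change alone is enough, provided it is fixed before outcomes are compared by arm.

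The cost is slightly more analysis work and no new data. The downside is sparse strata. With 92 evaluable patients spread evenly, 92/4 = 23 fall in each of four strata. If half are antibody-negative and 20% of those are not highly immunosuppressed, that stratum holds about 46 × 0.20 = 9. CMH tolerates this, and the extra strata cost a little efficiency if antibody level turns out not to predict response.
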